12.8.2.2.1 Temporary Suspension of Randomization and Dosing for ad hoc DSMB Safety Review

If any of the events listed in Section 12.8.2.2, *Ad hoc DSMB Reviews*, occur, the chair of the DSMB will be notified and a review of the safety data will be performed. The DSMB will have the discretion to recommend actions regarding study conduct, and will determine if enrollment in the study should be stopped and/or administration of study medications should be halted.

If a death occurs during the study, a temporary halt in consenting and screening of new participants as well as randomizing participants to Stage 2 will be implemented until after DSMB completes review of the safety data. Participants who have been consented and screened but not yet randomized into Stage 2 will be permitted to withdraw from their lupus medications per protocol during the randomization halt. If participants who have withdrawn from their lupus medications exceed their 28 day screening window during the ad hoc DSMB review period, an extension will be granted and the participant will be allowed to randomize once the ad hoc DSMB allows for resumption of randomization. Participants on study can continue with their assigned treatment, and participants deemed as a Stage 2 treatment failure at or before the Stage 2 week 24 can move into Stage 3 and be re-randomized.

If an ad hoc DSMB is called for excessive BILAG A flares or infections, the study will proceed as planned pending DSMB review of the data. However, if 2 weeks have elapsed and the DSMB has not met, then no new participants will be consented, screened, or randomized into Stage 2 until after the DSMB completes review of the safety data. Participants who have been consented and screened but not yet randomized into Stage 2 will be permitted to withdraw from their lupus medications per protocol during the randomization halt. If participants who have withdrawn from their lupus medications exceed their 28 day screening window during the ad hoc DSMB review period, an extension will be granted and the participant will be allowed to randomize once the ad hoc DSMB allows for resumption of randomization. Participants on study can continue with their assigned treatment, and participants deemed as a Stage 2 treatment failure at or before the Stage 2 week 24 can move into Stage 3 and be re-randomized.

13 Statistical Considerations and Analytical Plan

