3.1 Description of Study Design

This will be a multicenter, double blind, placebo-controlled Phase 2 trial of 120 participants with SLE who will enter with significant symptoms, but no organ-threatening disease. The study will be conducted in 3 stages.

3.1.1 Stage 1: Treatment Withdrawal:

During Stage 1, which may last up to 4 weeks, consenting participants will receive an IM injection of a long-acting corticosteroid, which may be repeated if needed to achieve amelioration of symptoms. A total of 3 corticosteroid injections may be given during Stage 1 with the first injection given as early as the Screening Visit after the mechanistic blood draw is completed and the last injection given as late as the Stage 2 Randomization Visit after the mechanistic blood draw is completed. Dose will be dependent on the available formulation.

In addition, participants will withdraw from all other treatments for lupus with the following exceptions: (i) PRN nonsteroidal anti-inflammatory treatments may be started or continued, (ii) PRN topicals may be continued, (iii) hydroxychloroquine, chloroquine, or quinacrine may be continued at any stable dose, and (iv) prednisone, if ≤ 10 mg/day, may be continued at stable doses but not started. Participants may screen if taking up to 20 mg/day prednisone (or equivalent) but both the participant and the investigator must be willing and able to taper to 10 mg/day (under cover of long-acting corticosteroids) by the Stage 2 Randomization Visit. Withdrawal of background lupus medications can start any time after the first corticosteroid injection is given but must be completed by the Stage 2 Randomization Visit.

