3.6 Stratification, Randomization, and Blinding

For Stage 2 randomization, participants will be stratified by screening gene expression signature:

- Group 1: high interferon and high inflammation
- Group 2: low inflammation and high B Cells (interferon can be high or low)
- Group 3: other profiles not included in groups 1 or 2
- Group 4: gene expression signature results unavailable (e.g. due to shipping or laboratory error)

For Stage 3 re-randomization, participants will be stratified by the Stage 2 treatment assignment: MMF vs Placebo MMF along with whether or not a long-acting corticosteroid injection was given at the time of Stage 2 treatment failure.

The randomization will be performed by the Division of Allergy, Immunology, and Transplantation (DAIT) Statistical and Clinical Coordinating Center (SCCC). Blinding will be maintained for all study participants and trial personnel throughout the study, except for the study site pharmacist. Treatment assignments will be centrally randomized and communicated to the unblinded study site pharmacist. The investigators, clinic personnel, and participants will not be informed regarding the intervention assignment until the study is unblinded. Laboratories performing assays for this protocol will be blinded to the identity and group assignment of biological materials to be studied.

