5.4 Risks of Withdrawal of Lupus Medications

During Stage 1, consenting participants will withdraw from current lupus medications. Withdrawal of lupus medications per protocol prior to randomization into Stage 2 could lead to disease exacerbation or flare. After signing of consent, the participant will receive a corticosteroid injection, which may be repeated an additional 2 times to achieve amelioration of symptoms. The use of corticosteroid injections which naturally wane in their effects gradually is a mitigation strategy for these risks.

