8.1 Study Visits

8.1.1 Screening and Enrollment

The study will be explained in lay terms to each potential research participant. The potential participant will sign an IRB-approved informed consent form (ICF) before undergoing any study procedures. Once the ICF has been signed, the participant is considered enrolled in the study and will be assigned a unique participant number. At this time, study-specific procedures may be performed. Consented participants will receive an intramuscular injection of a long-acting corticosteroid at screening which may be repeated if needed to achieve amelioration of symptoms.

Withdrawal of background lupus medications can start any time after the first corticosteroid injection is given, but must be complete by the Stage 2 Randomization Visit.

The purpose of screening, which begins at the time of signed consent, is to confirm eligibility to enter the study. All screening procedures, assessments, and laboratory measures to determine participant eligibility will be conducted within a 28-day screening window. The assessment of eligibility may take a series of visits that occur on separate days. Blood draws for screening should be performed prior to initiation of any change of therapy, including corticosteroid injection(s) or withdrawal of background medications. The Screening Visit biomarkers should reflect, as much as possible, the biometrics of the participant prior to any study procedures. Participants with abnormal laboratory values that prohibit entry may be re-tested once during the screening, which may last up to 28 days. Participants who screen fail may be rescreened one time and must repeat all screening assessments. Any further rescreening activity requires approval by the medical monitor.

Participants who withdraw from their lupus medications and then screen fail prior to Stage 2 will have a safety follow-up visit 4 weeks \pm 10 days after the date of screen fail. Participants will then be treated by their rheumatologist per clinical judgment.

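### During a DSMB halt, screened participants may begin withdrawing lupus drugs while Stage 2 is closed, and the 28-day extension is stated only for those who have already withdrawn

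*Combined protocol and SAP*

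**What the plan says.** Section 12.8.2.2.1 has two halt paragraphs. A death stops consenting, screening and Stage 2 randomization until the DSMB completes its review. A review called for excess BILAG A flares or infections lets the study proceed, but the same stop applies if 2 weeks pass without a DSMB meeting. Neither paragraph states a maximum length.

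Both paragraphs then say that participants who are consented and screened but not yet randomized "will be permitted to withdraw from their lupus medications per protocol during the randomization halt". Both grant an extension under this condition: "If participants who have withdrawn from their lupus medications exceed their 28 day screening window during the ad hoc DSMB review period".

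The related rules are elsewhere:

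- Section 3.1.1: withdrawal "can start any time after the first corticosteroid injection is given but must be completed by the Stage 2 Randomization Visit". Up to 3 steroid injections are allowed in Stage 1.
- Section 5.4: "Withdrawal of lupus medications per protocol prior to randomization into Stage 2 could lead to disease exacerbation or flare". It presents the steroid injections as the mitigation.
- Section 8.1.1: the screening window is 28 days. On rescreening it says: "Participants who screen fail may be rescreened one time and must repeat all screening assessments". Beyond that one rescreen, the medical monitor has to approve.
- Section 8.1.1, on timing of samples: "Blood draws for screening should be performed prior to initiation of any change of therapy, including corticosteroid injection(s) or withdrawal of background medications".
- Section 3.6: "For Stage 2 randomization, participants will be stratified by screening gene expression signature".

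**The concern.** A halt separates withdrawal from its purpose. In normal running, a participant comes off background drugs because randomization follows within the window. During a halt, a participant can start withdrawal with no randomization date, and if the DSMB stops enrollment that participant has taken the risk without study drug or trial entry. One of the two halts is itself prompted by flares or infections.

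The extension wording leans the wrong way. Someone who has withdrawn has a written extension. Someone who waits on background drugs has none in writing. If a site treated that person as a screen failure at day 28, a rescreen would follow at least one steroid injection, provided the first was given at screening as section 8.1.1 describes. That sits badly with the request for screening blood before any change of therapy, with the active-disease requirement of inclusion criterion 3, and with use of the screening signature as the Stage 2 stratum.

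At stake are the safety of a few participants and clear instructions to sites. No effect on treatment failure rates is claimed.

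**Working it through.** The plan gives no figure to reproduce here. The check has two parts.

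**Reading the rules together**

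1. The permission covers everyone consented, screened and not randomized. It is not limited to people already part-way through withdrawal.
2. Withdrawal under the protocol may start at any time after the first injection (sections 3.1.1 and 8.1.1). Starting during a halt is therefore allowed, though not required.
3. Withdrawal must be complete by the Randomization Visit, and that visit cannot take place while randomization is closed. No minimum washout before it is set. Deferring therefore breaks no rule.
4. The extension is conditional on having withdrawn. No sentence grants or refuses one to anybody else.

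**Size**

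Inputs from the plan: 120 randomizations, 2.5 years to achieve them, and Stage 1 of up to 28 days. Assumptions: even accrual; withdrawal starting d = 7, 14 or 21 days after Screening (28 as an upper bound); halt length L = 2, 4 or 8 weeks; screen failure f = 20% to 50%.

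- Rate: 120 / (2.5 × 365.25) = 0.1314 eventual randomizers per day.
- Expected number in Stage 1 at once, at most: 0.1314 × 28 = 3.7. Counting later screen failures: 3.7 / (1 − f) = 4.6 (f = 0.2) to 7.4 (f = 0.5).
- Eventual randomizers who have not begun withdrawal when the halt starts: 0.1314 × d.
- Of these, the number passing day 28 if they stay on their drugs: 0.1314 × max(0, d − max(0, 28 − 7L)).

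| d (days) | Not yet begun | Past day 28, L = 2 | Past day 28, L = 4 or 8 |
|---|---|---|---|
| 7 | 0.9 | 0 | 0.9 |
| 14 | 1.8 | 0 | 1.8 |
| 21 | 2.8 | 0.9 | 2.8 |
| 28 (bound) | 3.7 | 1.8 | 3.7 |

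Someone who starts withdrawal during a halt of L weeks spends at most L weeks of it off drug: 2, 4 or 8 weeks. Section 1.2.2 says the earliest flares may start within a month and most come after 2 or 3 months, which is about 8.7 to 13 weeks. As a rough comparison, a 4-week halt reaches the earliest flares, and none of the assumed halts reaches the usual period.

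Injections left once withdrawal has begun: 3 − 1 = at most 2.

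**The case against.** The strongest defense is that this is a deliberate and permissive choice. The sponsor foresaw the halt, thought about people already injected with steroids, and avoided interrupting Stage 1. Section 1.2.2 gives reasons for early withdrawal: washout of interacting immunosuppressants improves safety, simpler background treatment helps interpretation, and drugs being taken at entry are by definition not controlling the disease. It also reads very early flares as a sign of too little steroid, which an unused injection can address. Deferral lets steroid cover wane before withdrawal starts. A wider extension lengthens the gap from Screening, which supplies the SRI and BICLA references, the CGI-C comparison for criterion 7 and the stratum.

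Part of this stands. Withdrawal is optional, and the longer gap and possible extra injection are real costs. Existing provisions also make a separate decision rule at day 28 unnecessary: unscheduled visits (8.1.6), investigator or medical monitor discretion (11.2), and the safety visit 4 weeks ± 10 days after screen failure for those who have withdrawn (8.1.1).

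The rest does not defeat the point. The protocol requires no minimum washout, so one completed after reopening still complies. Steroid cover wanes whether or not background drugs are stopped. The existing extension already ages the same Screening values. Section 5.4 still lists flare as a risk of withdrawal despite the argument in 1.2.2.

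A reader might infer that the plan denies an extension to those who stay on their drugs and forces them to rescreen. The documents do not say so. Section 12.8.2.2.1 is silent, and section 8.1.1 does not say that being held past day 28 by a halt is a screen failure. The condition could even be read as covering anyone who uses the permission. The rescreening sequence is only what could follow from that silence.

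**Conclusion.** The point holds as a gap in wording with a modest patient-safety consequence. Both halt paragraphs permit new withdrawals during a closure of unstated length, and both state the extension only for those who have withdrawn. The text of both paragraphs is clear on this.

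The size is small: about 1 to 3 eventual randomizers per halt not yet withdrawing, with an upper bound of 3.7. In a 2-week halt, 0, 0 or 0.9 of them would pass day 28 for withdrawal starting on day 7, 14 or 21; in a halt of 4 weeks or more, all would. These counts rest on even accrual and on assumed withdrawal timing and halt length. The documents do not say how often a halt would occur.

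A reader might also infer that the plan obliges participants to withdraw during a halt, or that the trial's comparison would be distorted. Neither is supported. The wording only permits withdrawal, and it applies before randomization, so it does not differ by arm. The change is worth making because it is cheap.

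**What to change.** In both halt paragraphs of section 12.8.2.2.1, state that:

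1. participants who have not begun withdrawing lupus drugs should defer it until the DSMB reopens randomization;
2. participants already withdrawing may continue;
3. the extension of the 28-day window applies to all consented and screened participants, with enough time after reopening to complete withdrawal under the remaining permitted Stage 1 injections.

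Item 3 also removes any need to rescreen after steroids. No separate rule at day 28 is needed.

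The cost is wording in two paragraphs, with no new procedure. About 1 to 3 participants per halt, on the assumed timing, may need a second or third permitted injection. They would be randomized later, with a longer gap from their Screening reference values, as the existing extension already allows.

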13.1 Overview

This is a multicenter, double blind, placebo-controlled clinical trial of participants with non-organ-threatening SLE. The study will be conducted in 3 stages. Stage 1 will be a treatment withdrawal phase where participants must demonstrate adequate improvement with long-acting corticosteroids in order to proceed to Stage 2. Stage 2 will be a randomization phase comparing MMF versus corresponding MMF placebo. The purpose of Stage 2 is to assess the primary endpoint, which investigates the effectiveness of 24 weeks of MMF within previously identified immunologically-homogenous subsets of SLE patients. Stage 3 is a re-randomization phase comparing MMF plus voclosporin or MMF plus placebo for voclosporin. Stage 3 is intended to be an exploratory investigation of baseline gene expression patterns and their associations with response.

13.2 Endpoints

Endpoints are listed in Sections 3.2, *Primary Endpoint*, 3.3, *Secondary Endpoints*, and 3.4, *Exploratory Endpoints*.

13.3 Measures to Minimize Bias

The following measures will be employed to minimize bias:

- Randomization to treatment assignment to avoid selection bias.
- Double blind design to avoid ascertainment bias.
- Use of central laboratories for consistency in assay procedures and measurements for clinical and mechanistic endpoints.

13.4 Analysis Plan

13.4.1 Analysis Populations

13.4.1.1 Stage 2 Analysis Populations

Modified Intent to Treat Population:

The modified Intent-to-Treat population (mITT) will consist of all Stage 2 randomized participants who received at least one dose of MMF or MMF placebo. The mITT population will be used for all Stage 2 efficacy analyses and will include participants under the treatment to which they were randomized, regardless of compliance with assigned treatment.

Per Protocol Populations:

Two per protocol (PP) populations will be defined for Stage 2 analyses.

The PP1 population will consist of mITT participants who:

- Have either completed the Stage 2 Week 24 visit without experiencing a Stage 2 failure or have experienced a treatment failure on or prior to Stage 2 Week 24;
- Have $\geq 80\%$ compliance with MMF or MMF placebo administration from randomization through the Stage 2 Week 24 visit or until treatment failure (whichever comes first), where compliance is assessed by numbers of capsules of study product returned to the site;
- Have no protocol violations or ineligible entry criteria deemed likely to affect the efficacy outcomes of interest either through Week 24 of Stage 2 or treatment failure (whichever comes first).

The PP2 population will consist of mITT participants who:

- Have either completed the Stage 2 Week 48 visit without experiencing a Stage 2 failure or have experienced a treatment failure on or prior to Stage 2 Week 48;
- Have $\geq 80\%$ compliance with MMF or MMF placebo administration from randomization through the Stage 2 Week 48 visit or until treatment failure (whichever comes first), where compliance is assessed by numbers of capsules of study product returned to the site;
- Have no protocol violations or ineligible entry criteria deemed likely to affect the efficacy outcomes of interest either through Week 48 of Stage 2 or treatment failure.

A blinded data review panel will evaluate deviations from the protocol including, for example, violations of entry criteria, departures from assigned treatment regimen, modifications of concurrent therapy, failure to complete study visits, or administration of study procedures outside the specified visit windows to determine if occurrence of these deviations should exclude participants from the PP1 or PP2 population.

The PP1 population will be used for the Stage 2 analysis of the primary endpoint and secondary/exploratory endpoints assessed at Stage 2 Week 24, the PP2 population will be used in the analyses of the secondary/exploratory Stage 2 efficacy endpoints which are assessed over the entire 48 week treatment period.

13.4.1.2 Stage 3 Analysis Populations

Modified Intent to Treat Population:

The Stage 3 modified Intent-to-Treat population (mITT3) will consist of all Stage 3 randomized participants who received at least one dose of MMF plus voclosporin or MMF plus placebo for voclosporin. The mITT3 population will be used for all Stage 3 efficacy analyses and will include participants under the treatment to which they were randomized, regardless of compliance with assigned treatment.

Per Protocol Population:

The Stage 3 PP population (PP3) will consist of mITT3 participants who:

- Have either completed the Stage 3 Week 24 visit without experiencing a Stage 3 failure or have experienced a treatment failure on or prior to Stage 3 Week 24;

- Have $\geq 80\%$ compliance with MMF + voclosporin or MMF + placebo for voclosporin administration from randomization through the Stage 3 Week 24 visit or until treatment failure (whichever comes first), where compliance is assessed by numbers of capsules of study product returned to the site;
- Have no protocol violations or ineligible entry criteria deemed likely to affect the efficacy outcomes of interest throughout the entire study.

A blinded data review panel will evaluate deviations from the protocol including, for example, violations of entry criteria, departures from assigned treatment regimen, modifications of concurrent therapy, failure to complete study visits, or administration of study procedures outside the specified visit windows to determine if occurrence of these deviations should exclude participants from the PP3 population.

The PP3 population will be used in the analyses of the Stage 3 secondary efficacy endpoints.

13.4.1.3 Safety Population

The safety population will include all participants who receive at least one IM injection of a long-acting corticosteroid or who initiate withdrawal of lupus medications in Stage 1. The safety population will be used for all safety analyses. Analysis performed on the safety population will be according to the treatment actually received in both Stage 2 and Stage 3.

13.4.2 Primary Analysis of Primary Endpoint

The primary endpoint is the cumulative incidence of treatment failure at or before the Stage 2 Week 24 visit. Time to treatment failure is defined as the interval from the day of Stage 2 randomization until the day of treatment failure (as defined in Section 3.2, Primary Endpoint). Participants who withdraw from the study early without evidence of treatment failure will be censored at day of the last assessment they were determined to be failure-free. The risk of treatment failure over the period of Stage 2 randomization through 24 weeks of follow-up will be presented graphically using Kaplan-Meier product limit estimates of the survival function in subgroups defined by treatment arm and by immunologically-homogenous subsets. The Kaplan-Meier estimates of event-free survival and confidence intervals using Greenwood's formula for standard error will be reported by subgroup at Stage 2 Week 24. The primary analysis will be a stratified two-sample test of the cumulative incidence of treatment failure at Stage 2 Week 24 using a 2-sided $\alpha=0.05$.

The ultimate goal of Stage 2 is to evaluate the potential effectiveness of MMF within the 7 previously-identified immunologically-homogeneous clusters for lupus. Regardless of the outcome of the stratified test for the pooled analysis, within-cluster landmark two-sample tests will be performed for comparisons of the cumulative incidence of treatment failure at Stage 2 Week 24 for each cluster. Due to the limited samples sizes anticipated in each immunologically-defined subgroup, no correction for multiple comparisons will be made, and p-values of < 0.10 will be considered notable findings but will be interpreted with caution given the high probability of a family-wise error with multiple comparisons under a strong null hypothesis of no treatment benefit.

